15.8 Protocol Amendments

Any amendments or administrative changes in the research protocol during the period, for which the IRB approval has already been given, will not be initiated without submission of an amendment for IRB review and approval.

These requirements for approval will in no way prevent any immediate action from being taken by the investigator in the interests of preserving the safety of all subjects included in the trial.

Any amendments to the protocol that significantly affect the safety of subjects, scope of the investigation, or the scientific quality of the study are required to submit the amendment for FDA review.

15.9 Protocol Deviations

A protocol deviation (or violation) is any departure from the defined procedures and treatment plans as outlined in the protocol version submitted and previously approved by the IRB. Protocol deviations have the potential to place participants at risk and can also undermine the scientific integrity of the study thus jeopardizing the justification for the research. Protocol deviations are unplanned and unintentional events.

Because some protocol deviations pose no conceivable threat to participant safety or scientific integrity, reporting is left to the discretion of the PI within the context of the guidelines below. The IRB requires the **prompt reporting** of protocol deviations which are:

- Exceptions to eligibility criteria.
- Intended to eliminate apparent immediate hazard to a research participant or
- Harmful (caused harm to participants or others, or place them at increased risk of harm - including physical, psychological, economic, or social harm), or
- Possible serious or continued noncompliance

15.10 FDA Annual Reporting

This study is IND exempt therefore there are no annual reporting requirements to the FDA.

15.11 Clinical Trials Data Bank

The study will be registered on <http://clinicaltrials.gov> and the NCI CTRP (Clinical Trials Reporting Program) by the Clinical Trials Office.

15.12 Record Keeping

Per 21 CFR 312.57, the Investigator records shall be maintained for a period of 2 years following the date a marketing application is approved; or, if no application is filed or the application is not approved, until 2 years after the investigation is discontinued and the FDA is notified.

Appendix A – Radiation Therapy Oncology Group (RTOG) toxicity grading system

Patient ID: _____

Date: _____

Time point: _____

0	1	2	3	4	5
No symptoms	Minor symptoms requiring no treatment	Symptoms responding to simple outpatient management, lifestyle (performance status) not affected	Distressing symptoms altering the patient's lifestyle (performance status) Hospitalization for diagnosis or minor surgical intervention (such as urethral dilation) may be required	Major surgical intervention (such as laparotomy, colostomy, cystectomy) or prolonged hospitalization required	Fatal complications

Physician signature: _____

Date: _____

Appendix B – Clavien-Dindo Classification of Surgical Complication

Grade	Definition
Grade I	Any deviation from the normal postoperative course without the need for pharmacological treatment or surgical, endoscopic, and radiological interventions Allowed therapeutic regimens are: drugs as antiemetics, antipyretics, analgetics, diuretics, electrolytes, and physiotherapy. This grade also includes wound infections opened at the bedside
Grade II	Requiring pharmacological treatment with drugs other than such allowed for grade I complications Blood transfusions and total parenteral nutrition are also included
Grade III	Requiring surgical, endoscopic or radiological intervention
Grade IIIa	Intervention not under general anesthesia
Grade IIIb	Intervention under general anesthesia
Grade IV	Life-threatening complication (including CNS complications)* requiring IC/ICU management
Grade IVa	Single organ dysfunction (including dialysis)
Grade IVb	Multiorgan dysfunction
Grade V	Death of a patient
Suffix “d”	If the patient suffers from a complication at the time of discharge (see examples in Table 2), the suffix “d” (for “disability”) is added to the respective grade of complication. This label indicates the need for a follow-up to fully evaluate the complication.

*Brain hemorrhage, ischemic stroke, subarachnoidal bleeding, but excluding transient ischemic attacks.

CNS, central nervous system; IC, intermediate care; ICU, intensive care unit.

Appendix C – FACT-P Questionnaire

Patient ID: _____

Date: _____

Time point: _____

Below is a list of statements that other people with your illness have said are important. **Please circle or mark one number per line to indicate your response as it applies to the past 7 days.**

	PHYSICAL WELL-BEING	Not at all	A little bit	Some-what	Quite a bit	Very much
GP1	I have a lack of energy	0	1	2	3	4
GP2	I have nausea	0	1	2	3	4
GP3	Because of my physical condition, I have trouble meeting the needs of my family	0	1	2	3	4
GP4	I have pain	0	1	2	3	4
GP5	I am bothered by side effects of treatment	0	1	2	3	4
GP6	I feel ill	0	1	2	3	4
GP7	I am forced to spend time in bed	0	1	2	3	4
	SOCIAL/FAMILY WELL-BEING	Not at all	A little bit	Some-what	Quite a bit	Very much
GS1	I feel close to my friends	0	1	2	3	4
GS2	I get emotional support from my family	0	1	2	3	4
GS3	I get support from my friends	0	1	2	3	4
GS4	My family has accepted my illness	0	1	2	3	4
GS5	I am satisfied with family communication about my illness	0	1	2	3	4
GS6	I feel close to my partner (or the person who is my main support)	0	1	2	3	4
Q1	Regardless of your current level of sexual activity, please answer the following question. If you prefer not to answer it, please mark this box  and go to the next section.					
GS7	I am satisfied with my sex life	0	1	2	3	4

FACT-P Questionnaire (page 2/3)

EMOTIONAL WELL-BEING		Not at all	A little bit	Some-what	Quite a bit	Very much
GE1	I feel sad	0	1	2	3	4
GE2	I am satisfied with how I am coping with my illness.....	0	1	2	3	4
GE3	I am losing hope in the fight against my illness.....	0	1	2	3	4
GE4	I feel nervous.....	0	1	2	3	4
GE5	I worry about dying.....	0	1	2	3	4
GE6	I worry that my condition will get worse	0	1	2	3	4
FUNCTIONAL WELL-BEING		Not at all	A little bit	Some-what	Quite a bit	Very much
GF1	I am able to work (include work at home)	0	1	2	3	4
GF2	My work (include work at home) is fulfilling.....	0	1	2	3	4
GF3	I am able to enjoy life.....	0	1	2	3	4
GF4	I have accepted my illness.....	0	1	2	3	4
GF5	I am sleeping well	0	1	2	3	4
GF6	I am enjoying the things I usually do for fun	0	1	2	3	4
GF7	I am content with the quality of my life right now.....	0	1	2	3	4

FACT-P Questionnaire (page 3/3)

ADDITIONAL CONCERNS		Not at all	A little bit	Some-what	Quite a bit	Very much
C2	I am losing weight.....	0	1	2	3	4
C6	I have a good appetite	0	1	2	3	4
P1	I have aches and pains that bother me.....	0	1	2	3	4
P2	I have certain parts of my body where I experience pain....	0	1	2	3	4
P3	My pain keeps me from doing things I want to do	0	1	2	3	4
P4	I am satisfied with my present comfort level	0	1	2	3	4
P5	I am able to feel like a man	0	1	2	3	4
P6	I have trouble moving my bowels.....	0	1	2	3	4
P7	I have difficulty urinating.....	0	1	2	3	4
BL2	I urinate more frequently than usual	0	1	2	3	4
P8	My problems with urinating limit my activities.....	0	1	2	3	4
BL5	I am able to have and maintain an erection.....	0	1	2	3	4

Subject signature: _____

Date: _____

Appendix D – Expanded Prostate Cancer Index Composite (EPIC-26)

Patient ID: _____ Date: _____ Time point: _____

This questionnaire is designed to measure Quality of Life issues in patients with Prostate cancer. To help us get the most accurate measurement, it is important that you answer all questions honestly and completely.

1. Over the **past 4 weeks**, how often have you leaked urine?

More than once a day.....	1	
About once a day.....	2	
More than once a week.....	3	(Circle one number)
About once a week.....	4	
Rarely or never.....	5	

23/

2. Which of the following best describes your urinary control **during the last 4 weeks**?

No urinary control whatsoever.....	1	
Frequent dribbling.....	2	(Circle one number)
Occasional dribbling.....	3	
Total control.....	4	

26/

3. How many pads or adult diapers per day did you usually use to control leakage **during the last 4 weeks**?

None	0	
1 pad per day.....	1	
2 pads per day.....	2	(Circle one number)
3 or more pads per day.....	3	

27/

4. How big a problem, if any, has each of the following been for you **during the last 4 weeks**?

(Circle one number on each line)

	No Problem	Very Small Problem	Small Problem	Moderate Problem	Big Problem	
a. Dripping or leaking urine	0	1	2	3	4	28/
b. Pain or burning on urination.....	0	1	2	3	4	29/
c. Bleeding with urination.....	0	1	2	3	4	30/
d. Weak urine stream or incomplete emptying.....	0	1	2	3	4	31/
e. Need to urinate frequently during the day.....	0	1	2	3	4	33/

5. Overall, how big a problem has your urinary function been for you **during the last 4 weeks**?

No problem.....	1	
Very small problem.....	2	
Small problem.....	3	(Circle one number)
Moderate problem.....	4	
Big problem.....	5	

34/

Appendix D – Expanded Prostate Cancer Index Composite (EPIC-26) (page 2/3)

6. How big a problem, if any, has each of the following been for you? (Circle one number on each line)

	No Problem	Very Small Problem	Small Problem	Moderate Problem	Big Problem	
a. Urgency to have a bowel movement	0	1	2	3	4	49/
b. Increased frequency of bowel movements.....	0	1	2	3	4	50/
c. Losing control of your stools.....	0	1	2	3	4	52/
d. Bloody stools	0	1	2	3	4	53/
e. Abdominal/ Pelvic/Rectal pain...	0	1	2	3	4	54/

7. Overall, how big a problem have your bowel habits been for you **during the last 4 weeks?**

No problem.....	1					
Very small problem.....	2					
Small problem.....	3					
Moderate problem.....	4					
Big problem.....	5					

(Circle one number) 55/

8. How would you rate each of the following **during the last 4 weeks?** (Circle one number on each line)

	Very Poor to None	Poor	Fair	Good	Very Good	
a. Your ability to have an erection?.....	1	2	3	4	5	57/
b. Your ability to reach orgasm (climax)?.....	1	2	3	4	5	58/

9. How would you describe the usual **QUALITY** of your erections **during the last 4 weeks?**

None at all.....	1					
Not firm enough for any sexual activity.....	2					
Firm enough for masturbation and foreplay only.....	3					
Firm enough for intercourse.....	4					

10. How would you describe the **FREQUENCY** of your erections **during the last 4 weeks?**

I NEVER had an erection when I wanted one.....	1					
I had an erection LESS THAN HALF the time I wanted one.....	2					
I had an erection ABOUT HALF the time I wanted one	3					
I had an erection MORE THAN HALF the time I wanted one.....	4					
I had an erection WHENEVER I wanted one.....	5					

Appendix D – Expanded Prostate Cancer Index Composite (EPIC-26) (page 3/3)

11. Overall, how would you rate your ability to function sexually **during the last 4 weeks?**

Very poor.....	1		
Poor.....	2		
Fair.....	3	(Circle one number)	64/
Good.....	4		
Very good.....	5		

12. Overall, how big a problem has your sexual function or lack of sexual function been for you **during the last 4 weeks?**

No problem.....	1		
Very small problem.....	2		
Small problem.....	3	(Circle one number)	68/
Moderate problem.....	4		
Big problem.....	5		

13. How big a problem **during the last 4 weeks**, if any, has each of the following been for you?

(Circle one number on each line)

	No Problem	Very Small Problem	Small Problem	Moderate Problem	Big Problem	
a. Hot flashes.....	0	1	2	3	4	74/
b. Breast tenderness/enlargement..	0	1	2	3	4	75/
c. Feeling depressed.....	0	1	2	3	4	77/
d. Lack of energy.....	0	1	2	3	4	78/
e. Change in body weight.....	0	1	2	3	4	79/

Subject signature: _____

Date: _____

Appendix E – Charlson Comorbidity Index

	Yes = 1	No = 0
Myocardial infarction History of definite or probable MI (EKG changes and/or enzyme changes)		
Congestive Heart Failure Exertional or paroxysmal nocturnal dyspnea and has responded to digitalis, diuretics, or afterload reducing agents		
Peripheral vascular disease Intermittent claudication or past bypass for chronic arterial insufficiency, history of gangrene or acute arterial insufficiency, or untreated thoracic or abdominal aneurysm (≥ 6 cm)		
Cardiovascular Accident (CVA) or Transient Ischemic Attack (TIA)		
Dementia Chronic cognitive deficit		
Chronic Obstructive Pulmonary Disease		
Connective tissue disease		
Peptic ulcer disease Any history of treatment for ulcer disease or history of ulcer bleeding		
	Yes = 2	No = 0
Hemiplegia		
Moderate to severe CKD Severe = on dialysis, status post kidney transplant, uremia, moderate = creatinine > 3 mg/dL (0.27 mmol/L)		
Leukemia		
Lymphoma		
	Yes = 6	No = 0
AIDS		
	Score	
Liver disease		

 • 0: None • +1: Mild = chronic hepatitis (or cirrhosis without portal hypertension) • +3: Moderate = cirrhosis and portal hypertension but no variceal bleeding history 		

+3: Severe = cirrhosis and portal hypertension with variceal bleeding history	
Diabetes mellitus 
0: None or diet-controlled+1: Uncomplicated+2: End-organ damage	
Solid tumor 
0: None+2: Localized+6: Metastatic	
Age 
0: < 50 years+1: 50-59 years+2: 60-69 years+3: 70-79 years+4: ≥ 80 years	

Total Score _____

Appendix F- Prostate Cancer Clinical Trials Working Group 3 (PCWG3)

The PCWG3 was created to more accurately assess bone lesions and to describe PSA based progression. PCWG3 rules were designed to be used in conjunction with radionuclide ($^{90}\text{m}\text{Tc}$) bone scintigraphy and therefore should be used for all bone response assessments. Only bone lesions seen on bone scans will be followed for assessment of response.

Bone Assessments

Baseline Assessment

All bone lesions may be recorded as non-target lesions only and the number of lesions should be noted.

Response Assessment

While on treatment, follow-up scans should be assessed for progressive disease (PD), progressive disease unconfirmed (P Du), no progressive disease (Non-PD), no evidence of disease (NED), or non-evaluable (NE).

Table 1: Bone response assessment categories

Bone Response	Definition
PD	2 new lesions, not flare, persistent
P Du	2 new lesions, but confirmation is required by the second scan. The temporary marker of PD should be updated to PD or non-PD upon subsequent scans. If P Du is determined on the last scan, sponsor should update to PD upon analysis.
Non-PD	At least 1 bone lesion present, but not enough to trigger PD.
NE	Status of bone lesions cannot be determined.
NED	No lesions are seen on bone scan (either none at baseline or all have resolved).

Rules of Progressive Disease

- 2+2 Rule: If 2 new lesions appear on the first scan after the initiation of treatment, the response is classified as P Du and another scan is performed ≥ 6 weeks.
 - If the next scans show at least 2 new bone lesions in addition to those seen in the prior scan, the prior scan is to be considered confirmed PD.
 - If the next scan does not show at least 2 additional new bone lesions the lesions seen on the prior scan are considered pre-existing lesions. The bone response on the prior scan is updated to non-PD and new lesions seen on the first scan are ignored.
- Once outside of the flare window (the first 12 weeks of treatment) the appearance of new lesions must be confirmed with a second scan ≥ 6 weeks after the first scan.
 - If ≥ 2 new lesions appear on a scan the scan will be classified as P Du until a second scan confirms lesion persistence.

- If lesions are persistent on the second scan, the prior response will be updated to PD.
- If the lesions disappeared on the second scan, the prior response is updated to non-PD.
- If 1 new bone lesion is seen on one scan classifying the scan as non-PD, but the following scan shows an additional new lesion (2 new lesions total between subsequent scans) the second scan will be classified as PD.
- Diffuse skeletal tumor involvement may result in a superscan. In this case, distinguishing between individual new bone lesions may be impossible. If a superscan occurs after baseline, the response will be considered PD and no further confirmation scans are required.

PSA Progression

PSA should be monitored at the beginning of every cycle. Any rise in PSA during the first 12 weeks of treatment should be monitored but should not be deemed evidence of progression. Record the percent change from baseline at 12 weeks. After a decline from baseline: record time from start of therapy to first PSA increase that is $\geq 25\%$ and ≥ 2 ng/mL above the nadir, and which is confirmed by a second value ≥ 3 weeks later (i.e., a confirmed rising trend).

Nodal and Soft Tissue Progression

Nodal and soft tissue documentation, tracking, and determination of progression will follow RECIST 1.1.

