⁹ PSA progression must be confirmed according to PCWG3 criteria, after at least 1 week. See Section 10.2.1.

¹⁰ To be performed at screening (within 90 days prior to enrollment).

¹¹ CT scans of the chest/abdomen/pelvis scans recommended to be performed 6 months and 1 year after completion of ALL treatments (salvage and adjuvant therapy) (\pm 2 weeks), and annually for 2 additional years (\pm 1 month) in patients without evidence of disease progression, otherwise as clinically indicated.

¹² Nuclear medicine bone scans recommended to be performed 6 months and 1 year after completion of ALL treatments (salvage and adjuvant therapy) (\pm 2 weeks), and annually for 2 additional years (\pm 1 month) in patients without evidence of disease progression, otherwise as clinically indicated.

¹³ TRUS biopsy must be performed at screening (within 1 year prior to enrollment) only for subjects who have been previously treated with definitive prostate radiotherapy and have disease recurrence in the prostate evidenced by positive molecular imaging (e.g., fluciclovine PET/CT or PSMA PET/CT scan or other per PI discretion).

¹⁴ Optional blood draws may be performed prior to starting salvage therapy, at the next standard of care follow up visit after completion of salvage therapy, and at the time of confirmed PSA progression or radiological progression. See Section 14.3 for details.

¹⁵ After completion of salvage treatment, optional blood will only be collected once at time of confirmed disease progression.

¹⁶ Optional archival tissue may be collected at baseline for all subjects for whom it is available. Archival tissue slides should not be cut until requested from the Central Lab. Lack of archival tissue will not be exclusionary.

¹⁷ Optional fresh tissue may be collected prior to starting salvage therapy during the TRUS biopsy (if performed) and at the time of oligometastasectomy or prostatectomy (if indicated and if available after SOC tissue collection). See Section 14.1 and 14.2 for details.

¹⁸ Quality of life (QOL) questionnaires (FACT-P and Expanded Prostate Cancer Index Composite EPIC-26) will be collected prior to starting salvage therapy, at the Response Assessment Visit, and at each follow-up visits. See Appendices C and D.

¹⁹To be performed at the Response Assessment Visit and at each follow-up visits See Appendix A.

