10.3 Time to Recurrence

CT scans and optional bone scans will take place every 6 months for the first year after completion of per-protocol directed therapy then annually thereafter for a total of 3 years.

The disease-free survival is defined as the time elapsed between study enrollment and first occurrence of confirmed radiographic disease progression as assessed according to the PCWG3 criteria (soft tissue by CT or MRI scans according to RECIST v1.1, bone metastasis by bone scan according to the PCWG3 criteria).

Soft tissue recurrence is defined by RECIST 1.1 as a $\geq 20\%$ increase and absolute ≥ 5 mm increase in the sum of diameters of target lesions (at most 5 lesions and 2 lesions per organ) OR the appearance of one or more new unequivocal lesions OR the unequivocal progression of existing non-target lesions. Soft tissue progression does not require confirmatory scans.

Bone progression is defined PCWG3 criteria as the appearance at any restaging scan of ≥ 2 new lesions which persist or increase at the confirmatory scan (to be performed ≥ 6 weeks later) OR, if ≥ 2 new lesions are observed at the first restaging scan, the appearance of ≥ 2 additional new lesions at the confirmatory scan (to be performed ≥ 6 weeks later).

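### Appendix F gives opposite bone-progression results for the first scheduled post-treatment bone scan, Section 10.3 does not settle which applies, and the last-scan rule in Appendix F conflicts with a confirmed endpoint

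*Combined protocol and SAP*

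**What the plan says.** **Section 10.3** defines bone progression by two limbs joined by OR. The first is the "appearance at any restaging scan of ≥ 2 new lesions which persist or increase at the confirmatory scan", with the confirmatory scan at least 6 weeks later. The second reads "if ≥ 2 new lesions are observed at the first restaging scan, the appearance of ≥ 2 additional new lesions at the confirmatory scan", with the same 6-week minimum.

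**Appendix F, 2+2 rule.** The trigger is "If 2 new lesions appear on the first scan after the initiation of treatment". If the next scan does not show at least two further lesions, "the lesions seen on the prior scan are considered pre-existing lesions", the earlier scan becomes non-PD and its new lesions are disregarded.

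**Appendix F, next rule.** "Once outside of the flare window (the first 12 weeks of treatment) the appearance of new lesions must be confirmed with a second scan", at least 6 weeks after the first. If the lesions persist, the earlier scan becomes PD.

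**Appendix F, Table 1.** PD is two new lesions that are not flare and that persist. For an unconfirmed progression on the last scan, the "sponsor should update to PD upon analysis".

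**Scan schedule.** Section 8.1, footnote 12, with matching footnotes in 8.2 and 8.3: "Nuclear medicine bone scans recommended to be performed 6 months and 1 year after completion of ALL treatments", within 2 weeks either way, then annually for two more years. Sections 9.3 and 10.3 call the follow-up bone scan optional. Section 9.1 also makes the screening bone scan optional.

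**Use of the definition.** Sections 1.2.3 and 11.3 analyse time from enrollment to confirmed radiographic progression by Kaplan-Meier, pooled and by arm. Section 6.4.1 uses radiographic progression per PCWG3 or RECIST 1.1 as an off-treatment criterion, after which follow-up is for toxicity only.

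**The concern.** A scan at 6 months after all treatment is both the first scan after treatment began and a scan taken after week 12. Two neighbouring rules in Appendix F then apply to it, and they disagree about persistent new lesions. Nothing in the documents says which takes precedence.

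What is at stake is the event status of individual patients in a planned secondary endpoint. One rule gives an event on the strength of the first restaging scan. The other gives no event and absorbs the lesions into the baseline, so a later event needs further new lesions. If the choice is left until the scans have been read, it becomes data-driven. Section 2 says the trial is meant to provide a reference for later studies, so an event definition that two readers would apply differently weakens its main use.

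The last-scan rule raises a second, separate question: whether an event that was never confirmed counts toward an endpoint defined by confirmation.

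**Working it through.** The plan states no figure on this point, so there is none to reproduce. The check has four steps.

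**1. Is the first scheduled scan outside the flare window?** Inputs: 6 months ± 2 weeks after all treatment (8.1 to 8.3); a 12-week window (Appendix F); radiotherapy of up to 8 weeks (Study Summary); adjuvant radiotherapy starting within 4 months of salvage therapy (6.2.3).

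- Weeks per month = 365.25 / 12 / 7 = 4.348. Six months = 26.1 weeks; four months = 17.4 weeks.
- Scan after the end of all treatment: 26.1 − 2 = 24.1 weeks to 26.1 + 2 = 28.1 weeks.
- Margin past the window, even if treatment took no time: 24.1 − 12 = 12.1 weeks.
- Counted from the start of treatment, Arm A with 8 weeks of radiotherapy: up to 28.1 + 8 = 36.1 weeks.
- Counted from the end of salvage therapy, with the full adjuvant delay and an assumed 8-week adjuvant course: up to 28.1 + 17.4 + 8 = 53.5 weeks.

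Every scan on schedule is therefore past week 12. Only an unscheduled, clinically indicated scan could fall inside the window.

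**2. What does each rule return?** Take two new lesions on that first scan and a confirmatory scan at least 6 weeks later.

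| First-scan lesions at confirmation | Further new lesions | 10.3, limbs joined by OR | 10.3, second limb only | App. F 2+2 rule | App. F rule after week 12 |
|---|---|---|---|---|---|
| Persist | 0 or 1 | PD | non-PD | non-PD | PD |
| Persist | 2 or more | PD | PD | PD | PD |
| Resolve | 0 or 1 | non-PD | non-PD | non-PD | non-PD |
| Resolve | 2 or more | PD | PD | PD | non-PD for the first scan |

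The first row is the conflict that matters. The last row also disagrees on a literal reading, but there the further lesions would open a new unconfirmed progression of their own, so the difference lies mainly in the date.

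**3. Are the results ordered sensibly?** Appendix F also says that one new lesion followed by one more on the next scan, two in all, is PD. Under the 2+2 rule, two persistent new lesions followed by one more, three in all, are non-PD. The patient with more new lesions is the one left event-free.

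**4. Size.** One subject in 20 is 1/20 = 5 percentage points of the pooled proportion at the time of that scan, measured from enrollment and before any censoring. Arm-level curves rest on fewer subjects, so each reclassification moves them more; arm sizes are not fixed. How many subjects would fall in the first row cannot be computed from the documents.

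**The case against.** **The Appendix F rules can be read as a sequence.** On this reading the 2+2 rule applies inside the window and persistence applies afterwards. That is plausible, and Table 1 fits it. But the 2+2 rule is tied to the first scan with no limit on how late that scan is, and no text gives the sequence. Making that reading binding needs the same wording change.

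**Section 10.3 may agree with the 2+2 rule.** A reader might infer that 10.3 plainly calls persistent first-scan lesions progression and that only Appendix F departs from it. The documents do not support that much. The second limb of 10.3 adds nothing for persistent lesions unless it was meant to replace the first limb at the first restaging scan. If it was, 10.3 sides with the 2+2 rule. The conflict inside Appendix F remains on either reading.

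**Size is easily overstated.** A reader might put 6-month recurrence-free at 17/20 = 85% under one rule and 20/20 = 100% under the other, supposing three affected subjects. Neither part is supported. The count of three has no source. The endpoint runs from enrollment, while the scan comes 6 months after treatment ends, so these events would generally fall after month 6 under either rule.

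**The reset need not erase real recurrences.** The screening bone scan is optional and entry is by molecular imaging, so a first follow-up bone scan may be a patient's first bone scan. Some lesions called new may indeed be old. This stands, and it means that counting on persistence carries an error of its own.

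**The last-scan rule sits under on-treatment wording.** Appendix F introduces its response categories for scans during treatment, and these scans come afterwards. But Appendix F also says its rules should be used for all bone response assessments, so the mismatch with a confirmed endpoint stays open.

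**Importance.** This is one secondary endpoint in a 20-subject descriptive pilot. The primary PSA endpoint is untouched. That limits the weight of the point; it does not remove the contradiction.

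**Conclusion.** The point holds as a contradiction in the current text. For a first restaging scan taken on schedule, two or more persistent new lesions with fewer than two further ones are non-PD under one rule in Appendix F and PD under the next. Section 10.3 does not resolve it. Table 1's last-scan update is a second, smaller conflict with an endpoint that requires confirmation.

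The effect is about 5 points of the pooled proportion per reclassified subject, assuming 20 subjects in the analysis and no earlier censoring or events. The total effect is unknown, because bone scans are optional or recommended, and it could be nil if no patient shows this pattern. The timing result assumes scans on the recommended schedule. The documents do not show that either rule gives the truer recurrence date, and this review does not say so. The point should be corrected before analysis; it does not threaten the primary endpoint.

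**What to change.** - **One rule.** Reconcile 10.3 and Appendix F so that a single endpoint rule, fixed before analysis, governs a first restaging scan taken after week 12. Limiting the 2+2 rule to scans inside the 12-week window would be consistent with Appendix F's own flare window and with the first limb of 10.3. If the second limb of 10.3 was meant to replace the first limb at that scan, the text should say so.
- **Event date.** State whether a confirmed bone progression is dated at the scan that first showed the lesions or at the confirmatory scan.
- **Last scan.** Reconcile Table 1 with the requirement for confirmation. Report time to recurrence with last-scan unconfirmed PD handled both ways, one as the main analysis and the other as sensitivity, and name in advance which is which.
- **Section 6.4.1.** The off-treatment criterion relies on the same PCWG3 definition, so these passages must be reconciled there too. Which clinical rule applies is for the investigators to decide.

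Cost: wording in 10.3, Appendix F and 6.4.1, plus one sensitivity analysis. No extra scans are needed, since confirmatory scans are already specified.
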